1.8.5.2 Clinical activity of donor-derived multivirus-directed VSTs

We evaluated the clinical utility of multivirus VSTs in recipients of matched related, matched unrelated, or haploidentical donor transplants. To date, 35 clinical-grade multivirus-directed VSTs have been generated from donor PBMCs. These lines were polyclonal, comprising both CD4+ (57±5%) and CD8+ (35±5%) cells and retained expression of the memory markers CD45RO+CD62L+ (58±8%). Their specificity was dependent on the prior viral exposure of the cell donor; 32/35 lines had activity against Adv, 20/35 against CMV, 26/35 against EBV, 18/35 against BK and 21/35 against HHV-6. None of the lines reacted against recipient PHA blasts – indicating lack of alloreactive potential in these rapidly generated lines.

We administered these multivirus-specific donor-derived VSTs to 10 allogeneic HSCT recipients in a dose escalation study; 4 on DL1 ($5 \times 10^6/m^2$), 4 on DL2 ($1 \times 10^7/m^2$) and 2 on DL3 ($2 \times 10^7/m^2$). There were no immediate infusion toxicities, and no de novo acute GvHD, demonstrating the in vivo safety of these mVST. Three patients received the cells as viral prophylaxis (days 38-43 post-HSCT) and none developed viral infections at up to 3 months post-treatment. The other 7 patients received the cells as treatment for one or more active infections between days 59-139 post-HSCT. Based on viral load measurements by day 42 post-infusion, the VSTs were successful in controlling active infections with CMV (1 complete (CR) and 1 partial response (PR)), EBV (2 CRs, including a case of frank PTLD); Adv (1 CR); HHV6 (1 CR); and BK (3 CR, 1 PR, 1NR). Of note, 3 BK virus responders had tissue disease with severe hemorrhagic cystitis and all had marked improvement or disappearance of hematuria following infusion. One patient subsequently had an episode of transient but severe bladder pain in association with inflammation seen on cystoscopy coincident with a 6 log fall in urine BK viral load. Our only non-responder was a patient with BK infection whose line lacked activity for this virus, likely reflecting the serostatus of the donor. In addition, 3 patients subsequently reactivated other viruses than those for which they were initially treated, but all cleared these infections by week 12, without the requirement for additional cell infusions (CMV: 1CR; EBV: 1CR; BK: 1CR; HHV6: 1CR). Finally, 1 patient received multivirus specific VSTs under a single patient protocol as an emergency treatment for widespread and bulky rituximab-resistant EBV-PTLD. Post VST treatment there was an immediate decline in the patient's EBV viral load with complete and sustained resolution of PTLD, coincident with an increase in circulating EBV-specific T cells. However, the profound anti-tumor activity mediated by the rapidly-expanding EBV-directed T cells also produced a transient

CHARMS Protocol v1.0 (10.30.13)	Version 5.0 (10.6.15)
Version 2.0 (12.09.13)	Version 6.0 (08.29.16)
Version 2.1 (03.07.14)	Version 7.0 (04.26.17)
Version 3.0 (06.17.14)	Version 8.0 (05.24.17)
Version 4.0 (11.06.14)	Version 9.0 (08.10.17)

systemic inflammatory response syndrome, which was controlled with steroids and anti-TNFR antibody, with no long term adverse effects.

Thus, infusion of donor-derived, multivirus specific VSTs generated with clinical grade pepmixes and infused either prophylactically or as treatment for one or more viral infections has been safe and is associated with the appearance of virus-reactive T cells in peripheral blood that have been able to control infection with all 5 targeted viruses.

1.9 Limitations of donor-derived virus specific VSTs

Despite the successful use of donor-derived multivirus-directed VSTs in these trials, there are some limitations to this approach. One problem is that virus-specific VST lines can only be generated from donors who had previously been exposed to a virus and therefore cannot be generated from seronegative donors or cord blood. There is increasing evidence over the last years that the use of younger donors is associated with improved engraftment, decreased relapse rates and improvements in overall and event-free survival in HSCT patients³⁹. However younger donors are also more likely to be seronegative for several of the targeted virus, which along with the expanding use of cord blood transplants increases the number of patients for which donor-derived VSTs cannot be generated. Another problem is that despite the significant decrease in the amount of time it takes to manufacture virus-specific VSTs with our pepmix-based method (decrease from ~3 months to just 10 days), this time frame is still too long for patients with more fulminant viral disease.

1.10 Most closely matched allogeneic virus-specific VSTs

An alternative approach that bypasses the need to grow VSTs for individual patients is to bank closely HLA-matched allogeneic VSTs that could be available as an “off the shelf” product. A concern with this approach is that the in vivo persistence of a mismatched product may be suboptimal after administration, as the recipient may generate an immune response to the non-shared HLA antigens. However, a number of studies have demonstrated the feasibility of this approach and reported clinical responses in the patients with EBV lymphoma arising after HSCT or solid organ transplant.^{40;41} In the first and largest multicenter study, Haque et al used banked polyclonal EBV-specific T-cell lines to treat EBV-PTLD after HSCT or solid organ transplantation and reported an overall response rate of 52% at 6 months. Similar results have been reported from Memorial Sloan Kettering with four of five PTLD patients achieving CR in response to third party EBV-specific T-cells. Of note none of these studies report an increased risk of GVHD.

More recently our group has applied this approach to treat patients with refractory CMV, Adenovirus and EBV infections post allogeneic HSCT. Lines were generated using adenovector-pp65 transduced monocytes and EBV-LCL and were either retained from our prior donor-specific clinical study or were newly generated from donors with known antiviral activity, including HLA homozygous donors identified by the National Marrow Donor Program. A total of 32 lines were produced and characterized, 18 of which were administered to the 50 study patients. The selection of lines for infusion was based on the specificity of the line for the target virus through a shared HLA allele, as well as the overall level of HLA match.

This study was open to allogeneic HSCT recipients with CMV, AdV, or EBV infection that had persisted for at least 7 days despite standard therapy. Patients who had a suitable VST line

CHARMS Protocol v1.0 (10.30.13)	Version 5.0 (10.6.15)
Version 2.0 (12.09.13)	Version 6.0 (08.29.16)
Version 2.1 (03.07.14)	Version 7.0 (04.26.17)
Version 3.0 (06.17.14)	Version 8.0 (05.24.17)
Version 4.0 (11.06.14)	Version 9.0 (08.10.17)

received an intravenous infusion of up to 2×10^7 VSTs/m² and were eligible for additional infusions at intervals of at least 2 weeks, in the event of a partial response (PR). Of the 50 patients who received VST infusions 23 received VSTs for persistent CMV, 18 for persistent adenovirus, and 9 for refractory EBV-PTLD. Five of the 50 treated patients withdrew from the study or died of their underlying disease.

From the bank of 32 VST lines a suitable line was identified for 90% of the screened patients within 24 hours. Of the 50 patients who were treated with these VSTs 74.0% had a CR or PR (73.9% for CMV, 77.8% for AdV, and 66.7% for EBV), including responses in 6 of 9 patients with refractory EBV-PTLD, and most of these responses (89%) were durable. By contrast 8 patients in the study for whom a line was not available and who continued with “standard therapy” demonstrated a 13% response rate, and 6 (75%) died of viral disease.

1.11 Risks of Administering Virus specific VSTs

1.11.1 Risk of Administering Donor-derived VSTs

We recently reviewed the infusion-related adverse events (AE) following administration of ex vivo-expanded T cell products (antigen-specific cytotoxic T lymphocytes, allodepleted T cells, and genetically modified T cells) on investigational new drug (IND) studies in our center⁴². From 1998 to 2008, we infused a total of 381 T cell products to 180 recipients, enrolled on 18 studies, receiving T cells targeting malignancies or post-transplant viral infections. There were no grade 3-4 infusion reactions during initial monitoring or 24-h follow-up. Twenty-four mild (grade 1-2) AE occurred in 21 infusions either during or immediately following infusion (up to 6hrs), most commonly nausea and vomiting (41.6%), probably because of the dimethyl sulfoxide cryoprotectant, and hypotension (20.8%), attributable to diphenhydramine pre-medication. Twenty-two additional non-severe events were reported within 24 h of infusion, most commonly culture-negative fever, chills and nausea. An increased risk of AEs was associated with age [incidence rate ratio (IRR) 0.98; 95% confidence interval (CI) 0.96-1.00, P = 0.05], while an increased risk of immediate infusion-related events was higher in patients reporting allergies (IRR 2.72, 95% CI 1.00-7.40, P = 0.05); sex, disease type and T cell source (allogeneic or autologous) had no effect on frequency of adverse events⁴².

1.11.2 Risk of 3rd party VSTs

In a study at Memorial Sloan Kettering 5 patients received a median of 5 doses of third party virus specific VSTs for EBV after HSCT for EBV LPD, most at 1×10^6 EBV-VST/kg/infusion, and all infusions were well tolerated⁴⁴. Updated data from the study was reported recently at the American Society of Hematology meeting 2012, with now 10 patients after HSCT enrolled in this study and among the 10 patients one patient developed mild skin GVHD after infusion with 3rd party EBV-VSTs, but tolerated a subsequent infusion of EBV-VSTs from an alternate 3rd party donor, with no other incidences of GVHD reported.

In our study of third party VSTs specific for three viruses (AdV, CMV and EBV) a total of 50 patients were infused with third party banked VSTs. All of the infusions were well tolerated. There were no immediate adverse effects, and despite the HLA disparity between the VSTs and recipients, de novo GVHD occurred in only 2 patients (grade I in each case). In the 8 patients in whom acute GVHD developed within 45 days of the first infusion (grade I in 6 patients, grade II in 1 patient, and grade III in 1 patient), 6 had a history of GVHD prior to receiving the VSTs. An additional patient had a flare of chronic skin GVHD. Two patients experienced transplant-associated microangiopathy, a complication that occurs in up to 10% of HSCT recipients, particularly in those receiving sirolimus⁴⁵, as were both of our patients. Only 1 patient had secondary graft failure, concomitant with leukemic relapse.

In order to minimize the risk of infusing a VST product with alloreactive potential in our studies of donor-derived VSTs we have screened lines for reactivity against other host tissues such as fibroblasts and/or PHA blasts as a release criteria. However, there is no completely reliable in vitro assay for excluding the possibility of alloreactivity and performing such an assay in the current protocol would be difficult for two reasons. First, many recipients would not have residual pre-transplant lymphocytes available to make PHA blasts and their blood at the time of study eligibility determination would be of donor origin and therefore not a valid predictive target. Second, it would add 10 days to the release time which would adversely affect feasibility and perhaps outcome. We do not therefore propose this assay as a release criterion. We will, however, take several additional precautions to minimize the risk of GVHD. First, any patient with pre-existing GVHD of \geq Grade 2 will be excluded from the study. Second, we will administer VSTs at a dose of 2×10^7 cells/m². This is a much smaller number of T cells than administered at the time of an unmanipulated marrow infusion.

CHARMS Protocol v1.0 (10.30.13)	Version 5.0 (10.6.15)
Version 2.0 (12.09.13)	Version 6.0 (08.29.16)
Version 2.1 (03.07.14)	Version 7.0 (04.26.17)
Version 3.0 (06.17.14)	Version 8.0 (05.24.17)
Version 4.0 (11.06.14)	Version 9.0 (08.10.17)

1.11.3 Cytokine Release Syndrome

There have been several reported SAEs associated with cytokine release syndrome (CRS) in patients who received T cells⁴⁶ or bispecific T-cell engagers⁴⁷. The majority of CRS have been reported after the infusion of CAR T cells⁴⁸⁻⁵⁰, but CRS can also occur after the infusion of conventional antigen-specific T cells⁵¹ or tumor infiltrating lymphocytes⁵². Patients will be monitored closely as per study calendar and assessed for evidence of incipient CRS (onset of fever, malaise and dyspnea) and treated promptly. Management of CRS will follow published guidelines^{46,53}, and is described in more detail in SOP F 05.11.XX and includes treatment options based on the clinical severity of the symptoms, such as oxygen, inotropic agents, IL-6 receptor antibody (4-8 mg/kg), TNF- α antibody (5-10 mg/kg), and/or steroids (1-2 mg/kg/day of methylprednisolone or equivalent).

1.12 Treatment of patients with JC Virus

Recently the first use of ex vivo expanded polyomavirus-specific CTLs has been reported with successful control of JCV-induced progressive multifocal leukoencephalopathy post-HSCT⁵⁴. Balduzzi and colleagues treated an HSCT patient with resistant JCV-associated progressive multifocal leukoencephalopathy (PML) using donor-derived JCV-specific CTLs, which were generated in vitro after stimulation with 15-mer peptides derived from the BK virus VP1 and large T viral proteins⁵⁵. After adoptive CTL infusion, virus-specific cytotoxic cells were detected in the peripheral blood, and coincided with JCV-DNA clearance in the cerebrospinal fluid. This case suggests that adoptive transfer of JCV-targeted CTLs may contribute to restore JCV-specific immune competence and control PML in transplanted patients. Given these promising results in the context of a complete lack of proven antiviral medications effective against JC virus and the potentially devastating complications associated with JC virus, patients with persistent JC virus infection will be eligible for this study.

2 STUDY DESIGN

2.1 Primary Objective

This trial is designed to evaluate the feasibility and safety of partially HLA-matched VSTs specific for five viruses in HSCT patients with persistent EBV, CMV, adenovirus, BK and/or HHV6 infections.

2.2 Rationale for Study Design

The primary purpose of this pilot study is to assess the safety of administering partially HLA-matched VSTs in transplant patients with BK virus, HHV6, EBV, CMV, and/or adenovirus infection. We have elected to use a dose of 2×10^7 VSTs/m², which has been shown to be safe and have clinical activity in a Phase I study using the same T cell product in the donor-specific setting. Because the persistence of adoptively transferred cells may be shorter using a partially HLA-matched banked VST product, we have included an option of administering additional doses in subjects that have a partial response after one dose.

It is unclear what degree of matching will be needed for clinical activity so we propose to allow infusion of lines that match at only one antigen, with expected antiviral activity against the infecting

CHARMS Protocol v1.0 (10.30.13)	Version 5.0 (10.6.15)
Version 2.0 (12.09.13)	Version 6.0 (08.29.16)
Version 2.1 (03.07.14)	Version 7.0 (04.26.17)
Version 3.0 (06.17.14)	Version 8.0 (05.24.17)
Version 4.0 (11.06.14)	Version 9.0 (08.10.17)

virus through this single shared allele, although preference will be given to lines matching at the most loci where anti-viral activity through a shared allele has been confirmed.

For CMV infection, standard therapy is well defined as antiviral agents with ganciclovir being the agent of choice and foscarnet or cidofovir being effective second line agents. For EBV infection, rituximab is the current treatment of choice for patients with CD20+ lymphoma. For patients with CD20- tumors there is no clear standard of therapy although most physicians would likely administer chemotherapy. There is also no clear standard therapy for adenovirus or BK virus, although there are reports of cidofovir having activity. We have therefore chosen to use cidofovir as standard therapy for both these infections although this requirement would be waived if the subject could not tolerate this agent due to nephrotoxicity. Ganciclovir, cidofovir, and foscarnet have variable in vitro activity against HHV-6, and may have a role in treating HHV-6-associated disease. Hence standard therapy will include treatment with one or more of these agents.

2.3 Eligibility

2.3.1 Inclusion Criteria

For Initial VSTs and subsequent infusions: patients will be eligible following any type of allogeneic transplant (*as defined 2.3.1.1*) if they have CMV, adenovirus, EBV, BK virus and/or HHV6 infection/disease persistent or recurrent despite 14 days of standard therapy (*as defined 2.3.1.2*) OR after failure of treatment (*as defined 2.3.1.2*) after 7 days of standard therapy OR if unable to tolerate standard therapy. Patients with persistent JC virus infection will be eligible as well.

1. Prior myeloablative or non-myeloablative allogeneic hematopoietic stem cell transplant using either bone marrow or peripheral blood stem cells or single or double cord blood.
2. Treatment of the following persistent or relapsed infections despite standard therapy;

a. CMV: Treatment of persistent or relapsed CMV disease or infection after standard therapy. For CMV infection, standard therapy is defined as antiviral therapy with ganciclovir, foscarnet or cidofovir.^{56,57}

- i. CMV disease: defined as the demonstration of CMV by biopsy specimen from visceral sites (by culture or histology) or the detection of CMV by culture or direct fluorescent antibody stain in bronchoalveolar lavage fluid in the presence of new or changing pulmonary infiltrates or changes consistent with CMV retinitis on ophthalmologic examination.
- ii. CMV infection: defined as the presence of CMV positivity as detected by PCR or pp65 antigenemia or culture from ONE site such as stool or blood or urine or nasopharynx.

Failure of antiviral therapy: defined as a rise or a fall of less than 50% in viral load in peripheral blood or any site of disease as measured by PCR or pp65 antigenemia after 7 days of antiviral therapy.

b. Adenovirus: Treatment of persistent adenovirus infection or disease despite standard therapy. Standard therapy is defined as antiviral therapy with cidofovir¹³ or an alternative antiviral agent if patient will not tolerate cidofovir therapy because of poor renal function.

CHARMS Protocol v1.0 (10.30.13)	Version 5.0 (10.6.15)
Version 2.0 (12.09.13)	Version 6.0 (08.29.16)
Version 2.1 (03.07.14)	Version 7.0 (04.26.17)
Version 3.0 (06.17.14)	Version 8.0 (05.24.17)
Version 4.0 (11.06.14)	Version 9.0 (08.10.17)

- i. Adenovirus infection: defined as the presence of adenoviral positivity as detected by PCR or culture from ONE site such as stool or blood or urine or nasopharynx.
- ii. Adenovirus disease: defined as the presence of adenoviral positivity as detected by PCR, DFA or culture from two or more sites such as stool or blood or urine or nasopharynx.
- iii. Failure of therapy: defined as a rise or a fall of less than 50% in viral load in peripheral blood or any site of disease as measured by PCR or any other quantitative assay) after 7 days of antiviral therapy.

c. EBV: For treatment of persistent EBV infection despite standard therapy. For EBV infection, standard therapy is defined as rituximab given at 375mg/m² in patients for 1-4 doses with a CD20+ve tumor.⁵⁸

- i. EBV infection: defined as
 1. Biopsy proven lymphoma with EBV genomes detected in tumor cells by immunocytochemistry or in situ PCR
 2. Or clinical or imaging findings consistent with EBV lymphoma and/or elevated EBV viral load in peripheral blood.
- ii. Failure of therapy is defined as
 1. Increase or less than 50% response at sites of disease for EBV lymphoma OR
 2. Increase or a fall of less than 50% in EBV viral load in peripheral blood or any site of disease after 1st dose of rituximab.

d. BK virus: Treatment of persistent BK virus infection or BK virus disease despite antiviral treatment with cidofovir or leflunomide. No clear standard treatment is defined (section 1.1.5). Cidofovir¹⁵ has been administered in low doses as well as high doses to HSCT patients with BK infections but no randomized trials are available proving its clinical efficacy. In small trials leflunomide had activity against BK virus¹⁷, therefore we will consider this agent an acceptable alternative to cidofovir, given the absence of a clear first line option.

- i. BK virus infection is defined as the presence of BK virus positivity as detected by PCR or culture in one site such as blood or urine.
- ii. BK virus disease is defined as the presence of BK virus detectable by culture or PCR in blood or urine or other body fluids and symptoms of disease including, but not limited to persistent microscopic or macroscopic hematuria or detectable BK virus in more than one site.
- iii. Failure of therapy is defined as a rise or a fall of less than 50% in viral load in peripheral blood or any site of disease as measured by PCR or any other quantitative assay) or worsening hematuria after 7 days of antiviral therapy.

e. HHV6: Treatment of persistent HHV6 infection or disease despite antiviral treatment with ganciclovir, cidofovir and foscarnet. No clear standard treatment is defined.

CHARMS Protocol v1.0 (10.30.13)	Version 5.0 (10.6.15)
Version 2.0 (12.09.13)	Version 6.0 (08.29.16)
Version 2.1 (03.07.14)	Version 7.0 (04.26.17)
Version 3.0 (06.17.14)	Version 8.0 (05.24.17)
Version 4.0 (11.06.14)	Version 9.0 (08.10.17)

Ganciclovir, cidofovir and foscarnet all have variable *in vitro* activity against HHV-6, and may have a role in treating HHV-6-associated disease – therefore antiviral treatment with one or more of these agents will be acceptable initial therapy.

- i. HHV6 virus infection is defined as the presence of elevated HHV-6 levels as detected by PCR or positive culture in one site such as CSF or blood.
- ii. HHV6 disease is defined as defined as the presence of HHV6 detectable by culture or PCR in one or more sites such as blood or CSF and symptoms of disease including symptoms of HHV6 encephalitis OR detectable HHV6 by PCR or culture in more than one site.
- iii. Failure of therapy is defined as a rise or a fall of less than 50% in viral load in peripheral blood or any site of disease (as measured by PCR or any other quantitative assay) after 7 days of antiviral therapy.

f. JC virus: Treatment of progressive or persistent JC virus infection or disease without suitable alternative treatment option. Pepmixes specific for antigens on adenovirus, EBV, CMV, HHV6 and BK virus are used to generate our multivirus-specific VSTs. No pepmix specific for the rare JC virus is used for generation of these CTLs, however given the high homology (>90%) between JC and BK and the fact that BK virus-specific T cells targeting VP1 and Large T (as targeted in our multivirus VSTs) have been administered to treat JCV-PML, resulting in viral clearance from the cerebrospinal fluid it is likely that our VSTs are efficacious against JC virus. Given the current lack of treatment options for JC virus infection or reactivation after HSCT and the risk of progression to JML, which is almost uniformly fatal, and the apparent activity of BK virus-directed T cells against JC virus infected cells, we propose including patients with progressive or persistent JC virus on this study, unless a suitable alternative therapy is available.

- i. JC virus infection is defined as the presence of elevated JC virus levels as detected by PCR or positive culture in one site such as CSF or blood.
- ii. JC virus disease is defined as defined as the presence of JC virus detectable by culture or PCR in one or more sites such as blood or CSF and symptoms of disease including symptoms of PML OR detectable JC virus by PCR or culture in more than one site.

3. Patients with multiple CMV, EBV, Adenovirus, HHV6 and BK virus infections are eligible given that each infection is persistent despite standard therapy as defined above. Patients with multiple infections with one or more reactivation and one or more controlled infection are eligible to enroll.
4. Clinical status at enrollment to allow tapering of steroids to equal or less than 0.5 mg/kg/day prednisone (or equivalent).
5. HgB>8.0

CHARMS Protocol v1.0 (10.30.13)	Version 5.0 (10.6.15)
Version 2.0 (12.09.13)	Version 6.0 (08.29.16)
Version 2.1 (03.07.14)	Version 7.0 (04.26.17)
Version 3.0 (06.17.14)	Version 8.0 (05.24.17)
Version 4.0 (11.06.14)	Version 9.0 (08.10.17)

6. Pulse oximetry of > 90% on room air
7. Available multivirus-specific VSTs
8. Negative pregnancy test in female patients if applicable (childbearing potential who have received a reduced intensity conditioning regimen).
9. Written informed consent and/or signed assent line from patient, parent or guardian.

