3.1.2 Antiviral Activity

Peripheral blood and, where relevant, stool and urine will be monitored for CMV, EBV, adenovirus, BK virus, JC virus and/or HHV6 viral load. For the infection under treatment response in viral load will be defined as follows:

Complete response: Return to normal range as defined by specific assay used and clinical signs and symptoms.

Partial response: Decrease in viral load of at least 50% from baseline or 50% improvement of clinical signs and symptoms

Mixed response: Decrease in viral load of at least 50% from baseline for one infection and an increase or no change in viral load for a second infection (only applicable for patients with two or more infections at baseline).

Stable disease: Changes insufficient to qualify as partial response or progression

Progression: Increase in viral load of at least 50% from baseline or dissemination to other sites of disease.

Viral response data will be reviewed by a consensus committee of investigators.

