5.2 Sample Size Determination and Design Characteristics

Frist, the study will conduct a single arm pilot study using a phase IIa design. Simon's two-stage Minimax design⁶⁰ will be used to for the single-arm pilot study. Under the null hypothesis that the VST is not active, the data from previous trials suggest that the true response rate is 20% in anti-viral activity, where a positive response is defined as the viral load reduction to the normal level for at least one of the 5 virus types (CMV, EBV, adenovirus, BK virus and HHV6) within 42 days following the initial treatment of VST.

Allowing a 5% type-I error and 90% power, the null hypothesis will be tested against a one-sided alternative that the true response rate is 40%. The maximum size is 45 eligible patients, defined as the patients who receive the VST infusion and who can finish the 42 days follow-up. We anticipate that most patients will finish the follow up and will allow a 10% drop out rate. Therefore, the maximum sample size is 50.

The phase IIa trial operates in two stages, where the first stage recruits 24 patients. The trial pauses at the end of the first stage to make the decision on whether to stop the trial early due to lack of enough efficacy for treating viral infection, according to the rule as follows. Of the 24 patients at the first stage, if 5 or fewer positive responses are observed, then the study will be stopped. Otherwise, 21 additional patients will be accrued to reach the goal of 45 accruals. At the end of the trial, the null hypothesis will be rejected, if 14 or more positive responses are observed in among the 45 patients. This design has 65.6% chance to stop early when the true response rate is 20%.

After the phase IIa trial suggests excellent clinical responses that warrant further investigation, the study will be expanded to recruit 30 additional patients to evaluate the viral reduction based HLA matching. We hypothesize the viral reduction among the low HLA matching group (1/8, 2/8, or 3/8 HLA matching) is not worse than the high HLA matching group (4/8, 5/8, 6/8, 7/8, or 8/8).

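### Section 5.2 does not say how patients with JC virus alone are handled: as written they count in the Simon test's 24 and 45 but can never be responders.

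*Combined protocol and SAP*

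**What the plan says.** **Eligibility.** Section 2.3.1 opens by admitting patients with any of five viruses that persist or recur despite standard therapy, and adds "Patients with persistent JC virus infection will be eligible as well". Item 2f of that section, the eligibility checklist and the study schema all treat JC virus as a qualifying infection in its own right.

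**General response definition.** Section 3.1.2 lists JC virus among the viral loads monitored and states: "For the infection under treatment response in viral load will be defined as follows". JC virus is therefore inside the general definition.

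**The test.** Section 5.2 uses "Simon's two-stage Minimax design". A positive response is a viral load reduced to normal for at least one of five named viruses: "CMV, EBV, adenovirus, BK virus and HHV6) within 42 days following the initial treatment of VST". JC virus is not among them. The 45 evaluable patients are those who are infused and can finish 42 days of follow-up. No other condition is attached. The trial stops if 5 or fewer of the first 24 respond, and the null hypothesis is rejected if 14 or more of 45 respond.

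**Design population.** Sections 2.1, 2.2 and 5.1 describe the study population in terms of the five viruses only. No section says how a JC-only patient is handled in the test.

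**The concern.** Three definitions do not line up. Eligibility and 3.1.2 cover six viruses, the responder definition in 5.2 covers five, and the denominator in 5.2 covers everyone infused and followed to day 42. A JC-only patient enters the denominator and cannot enter the numerator. If that patient clears JC virus with resolution of signs and symptoms, 3.1.2 scores a complete response and 5.2 scores a non-response.

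The count matters because it drives two decisions: whether the trial stops after stage 1, and whether phase IIa supports the 30-patient expansion. Each structural non-responder pushes the count towards stopping and against rejection. If the handling is left open, it may have to be settled for an individual patient when the count is already known and near 5 or 6 of 24, or 13 or 14 of 45.

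**Working it through.** **Inputs, all from 5.2.** Null rate: "the true response rate is 20% in anti-viral activity". Alternative: "tested against a one-sided alternative that the true response rate is 40"%. Error rates: "Allowing a 5% type-I error and 90% power". Stage 1: "the first stage recruits 24 patients", stop at ≤5. Stage 2: 21 more, reject at ≥14 of 45.

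**Step 1: reproduce the plan's figures.** With response probability p,

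P(reject) = Σ over x from 6 to 24 of P[Bin(24, p) = x] × P[Bin(21, p) ≥ 14 − x].

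- p = 0.40: power 0.9001 (stated 90%).
- p = 0.20: type I error 0.0483 (limit 5%).
- Early stopping at p = 0.20: P[Bin(24, 0.20) ≤ 5] = 0.6559 (stated 65.6%).
- A search over totals of 43, 44 and 45 finds no qualifying design below 45. At 45, the 24/5/45/13 design has the smallest expected sample size of those that qualify.
- Dropout: 45 / 0.90 = 50, as stated.

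The design is correctly computed.

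**Step 2: add JC-only patients.** Let j₁ of the first 24 and j₂ of the next 21 have JC virus alone. Each has response probability 0 under 5.2; the rest respond with probability p. The decision limits do not change:

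P(reject) = Σ over x from 6 to 24 − j₁ of P[Bin(24 − j₁, p) = x] × P[Bin(21 − j₂, p) ≥ 14 − x].

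The documents give no expected number of JC-only patients, so the counts below are assumptions.

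| JC-only among the 45 | Power, others at 40% | Type I error, others at 20% |
|---|---|---|
| 0 | 90.0% | 4.8% |
| 1 | 87.6% (stage 1) or 88.4% (stage 2) | 4.0% or 4.1% |
| 2 | 84.7% (both in stage 1) to 86.5% (both in stage 2) | 3.2% to 3.5% |
| 3 | 81.3% (all in stage 1) to 84.2% (all in stage 2) | 2.6% to 2.9% |

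**Step 3: wrong stopping at stage 1 when the others respond at 40%.** P[Bin(24 − j₁, 0.40) ≤ 5] is 4.0% for j₁ = 0, 5.4% for j₁ = 1 and 7.2% for j₁ = 2.

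**Step 4: sensitivity to the assumed rate.** With one JC-only patient, power is 92.1–92.7% if the others respond at 42%, and 96.2–96.7% at 45%. To hold 90% with one such patient, the others need a true rate of about 41.0% (patient in stage 1) or 40.7% (stage 2).

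**The case against.** A reader might infer that any JC-only enrolment makes the stated 90% power untrue. The documents do not support that, for three reasons.

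- The patient must be infused, complete 42 days and fall within the phase IIa 45. Someone treated only in the 30-patient expansion does not touch this test.
- Section 5.1 describes the design population as patients with one of five viruses. If that was meant to govern the test set, the problem disappears. But 5.2, which defines the 45, does not repeat the restriction, so the handling is unstated rather than plainly wrong.
- The 40% must be the rate among patients who can respond under the five-virus definition. If it was meant as the rate over all evaluable patients, JC-only included, power stays at about 90%. The text does not say which.

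A Minimax design is also chosen to just reach its target at a nominal alternative, so almost any departure takes it under 90%. That the margin is only 0.01 percentage points says little by itself, and Step 4 shows how quickly power recovers at slightly higher rates. Section 2.3.1 calls JC virus rare and limits entry to cases without a suitable alternative treatment. The bias is conservative. The primary endpoints are feasibility and safety, and antiviral response is secondary.

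All of this stands, and it limits the size of the point. It does not remove the mismatch: 5.2 followed literally still scores JC clearance as failure in a test that can stop the trial.

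**Conclusion.** The inconsistency is real and the point is minor. The losses in the table are conditional: they hold if such patients are in the phase IIa 45 and the others respond at 40%. With one JC-only patient the loss is 1.6 to 2.4 percentage points of power. The documents do not let anyone say how many there will be.

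The point is confined to JC virus alone, since a patient who also has one of the five listed viruses can still be a responder. There is no inflation of false positives, and nothing here invalidates the design, whose own figures reproduce.

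**What to change.** Add one sentence to 5.2: the 24 and the 45 are patients treated for at least one of the five listed viruses, in line with 5.1; patients treated for JC virus alone are reported descriptively for response and remain in the safety analysis. Eligibility does not change. With JC-only patients outside the test set, the power at 40% is again 90.0%.

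Replacing the five-virus list by a reference to 3.1.2 would not be a clean alternative. That section adds partial and mixed categories, and its complete response also involves clinical signs, whereas 5.2 tests normalisation of viral load only. Counting JC clearance would also restore 90% power only if JC-only patients respond at 40%. The documents give no support for that rate, and no JC-specific peptide mix is used to make the cells.

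The cost is that each JC-only patient takes one of the 50 places without contributing to the Simon test. The 10% dropout allowance leaves 50 − 45 = 5 spare places, so each such patient uses one of them.
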